7.2.2.5 Laboratory evaluations

Clinical laboratory analyses (hematology, fasting biochemistry (full or partial), fasting lipase, fasting amylase, fasting lipid panel/glucose/c-peptide, HbA1_C, coagulation, pregnancy test and urinalysis) are to be performed by the central laboratory. In case of urgent safety management of hyperglycemia, fasting or random blood glucose assessment may be done locally according to the schedule of assessments and collection plan outlined respectively in Table 7-1 and Table 7-5 for the Core Phase.

Note: as hyperglycemia typically occurs within the first weeks of treatment, blood glucose at Day 8 and Day 15 of Cycle 1 should be performed both locally and centrally for rapid availability for safety evaluation and dose adjustments.

Unscheduled local laboratory assessments may be performed if medically indicated to assess a (potential) adverse event or when the treating physician cannot wait for central laboratory results for decision making (e.g. dose modifications) during the Core Phase. In this particular situation, if possible, the blood sample obtained at the same time point should be submitted to the central laboratory for analysis in parallel with local analysis. During the Extension Phase, all labs will be sent to local laboratory for testing.

The results of the local laboratory during the Core Phase will be recorded in the eCRF if any of the following criteria are met:

- A treatment decision was made based on the local results, or
- Local lab results document an adverse event not reported by the central lab, or
- Local lab results document an adverse event severity is worse than the one reported by the central lab, or
- There are no concomitant central results available

At any time during the study, abnormal laboratory parameters which are clinically relevant and require an action to be taken with study treatment (e.g. require dose modification and/or interruption of study treatment, lead to clinical symptoms or signs, or require therapeutic intervention), whether specifically requested in the protocol or not, will be recorded on the AE eCRF page. Laboratory data will be summarized using the Common Terminology Criteria for Adverse events (CTCAE) version 4.03. Additional analyses are left to the discretion of the investigator.

Visit windows of +/- 7 days are allowed. Novartis must be provided with a copy of the local laboratory's certification (if applicable), and a tabulation of the normal ranges and units of each parameter collected in the eCRF. Any changes regarding normal ranges and units for laboratory values assessed during the study must be reported via an updated tabulation indicating the date of revalidation. Additionally, if at any time a patient has laboratory parameters obtained from a different laboratory, Novartis must be provided with a copy of the certification and a tabulation of the normal ranges and units for this laboratory as well. The investigator is responsible for reviewing all laboratory reports for patients in the study and evaluating any abnormalities for clinical significance.

Table 7-5 Central clinical laboratory parameters collection plan during Core Phase

Test Category	Test Name
Hematology	Hematocrit, Hemoglobin, MCH, MCHC, MCV, Platelets, Red blood cells, RBC morphology, White blood cells, - Differential (Basophils, Eosinophils, Lymphocytes, Monocytes, Neutrophils)
Chemistry (Full)	Calcium, Magnesium, Potassium, Sodium, C-peptide, Alkaline phosphatase, ALT (SGPT), AST (SGOT), Direct Bilirubin, Indirect Bilirubin, Total Bilirubin, Gamma-glutamyl-transferase (GGT), Total Protein, Albumin, Creatinine, Creatine kinase (CK), Blood Urea Nitrogen (BUN) or Urea, Uric Acid, Lactate dehydrogenase (LDH),
Chemistry (Partial)	Creatinine, Creatine kinase, ALT, AST, Total Bilirubin
Fasting Lipid panel	Total Cholesterol, LDL, HDL, Triglycerides
Coagulation	International normalized ratio (INR) and Activated partial thromboplastin time (aPTT) or Partial thromboplastin time (PTT)
Pregnancy	Serum and Urine
Urinalysis	Macroscopic Panel (Dipstick) (WBC, blood, protein and glucose)
Additional tests	Amylase fasting, Lipase fasting, HbA1c, FG, RBG, FSH, estradiol

All laboratory analysis will be performed centrally during the Core Phase; however for urgent safety management or inclusion criteria, laboratory assessments may be allowed to be done locally and entered on an unscheduled local eCRF page (laboratory assessment performed locally should be sent to central laboratory as well for central analysis). During the Extension Phase, all laboratory assessments needed will be done via local laboratory testing.

Note: Fasting plasma glucose at Day 8 and Day 15 of Cycle 1 should be performed both locally and centrally for rapid availability for safety evaluation and dose adjustments.

A central laboratory will be used for analysis of all specimens collected during the Core Phase. Details on the collections, shipment of samples and reporting of results by the central laboratory are provided to investigators in the [Laboratory Manual].

7.2.2.5.1 Hematology

Hematology tests are to be performed by the central laboratory according to the schedule of assessments and collection plan outlined respectively in Table 7-1 during the Core Phase and Table 7-5. The Hematology panel specifics are listed in Table 7-5.

7.2.2.5.2 Clinical chemistry

Biochemistry tests are to be performed by the central laboratory according to the schedule of assessments and collection plan outlined respectively in Table 7-1 during the Core Phase and Table 7-5. The full biochemistry panel specifics are listed in Table 7-5.

7.2.2.5.3 Monitoring fasting plasma glucose, random blood glucose, c-peptide, fasting lipid panel, amylase, lipase and HbA1C

Fasting c-peptide, amylase, lipase, HBA1C and lipid panel will be assessed by the central laboratory according to the schedule of assessments and collection plan outlined respectively

in Table 7-1 and Table 7-5 for the Core Phase. Patients must be fasting overnight for 8 to 12 hours prior to the blood draw. The study personnel will ask the patient whether she/he has been fasting, which will be captured in the eCRF as well.

Beginning with C1D8 until EOT of Core Phase, patients can have RBG testing, at the discretion of the PI.

7.2.2.5.4 Coagulation

INR and PTT or aPTT will be assessed by the central laboratory according to the schedule of assessments and collection plan during the Core Phase outlined respectively in Table 7-1 and Table 7-5.

7.2.2.5.5 Urinalysis

Urinalysis dipstick analysis (WBC, blood, protein and glucose) will be performed by the central laboratory according to Table 7-1 during the Core Phase. The full urinalysis panel specifics are listed in Table 7-5.

7.2.2.5.6 Pregnancy and Hormone Levels

Pregnancy tests are to be performed according to the Visit Evaluation Schedule for the Core Phase and Extension Phase as outlined in Table 7-1, Table 7-2 and Table 7-5.

If participants cannot visit the site to have serum pregnancy tests during a Public Health emergency as declared by Local or Regional authorities i.e. pandemic, epidemic or natural disaster, that limits or prevents on-site study visits, urine pregnancy test kits may be used. Relevant participants can perform the urine pregnancy test at home and report the result to the site. It is important that participants are instructed to perform the urine pregnancy test first and only if the test result is negative proceed with the administration of the study treatment. A communication process should be established with the participant so that the Site is informed and can verify the pregnancy test results (e.g., following country specific measures)

A positive urine test is required to be confirmed by an immediate serum pregnancy test. A positive pregnancy test requires immediate interruption of study treatment until the assessment is confirmed. If positive, the patient must be discontinued from the study.

FSH and/or estradiol will be collected centrally and used for screening and confirmation of menopausal status during the Core Phase.

A condom is required for all sexually active male participants to prevent them from fathering a child AND to prevent delivery of study treatment via seminal fluid to their partner. In addition, male participants should not donate sperm for the time period specified above'.

All pre-menopausal women who are not surgically sterile will have pregnancy testing. Additional pregnancy testing might be performed if requested by local requirements'.

Assessments of fertility:-'Medical documentation of oophorectomy, hysterectomy, or tubal ligation must be retained as source documents. Subsequent hormone level assessment to confirm the woman is not of child-bearing potential must also be available as source documentation in the following cases:

- 1. Surgical bilateral oophorectomy without a hysterectomy
- 2. Reported 12 months of natural (spontaneous) amenorrhea with an appropriate clinical profile.

In the absence of the above medical documentation, FSH testing is required of any female participant regardless of reported reproductive/menopausal status at screening/baseline'.

7.2.2.6 Radiological examinations

In case of pneumonitis, patients will be monitored carefully according to Section 6.3.2.1.1. If pneumonitis develops during treatment in the Core Phase, additional chest CT scan or x-ray may be performed to follow-up on the event.

7.2.2.7 Cardiac assessments

7.2.2.7.1 Electrocardiogram (ECG)

A standard 12 lead ECG will be performed after the patient has been resting for 5-10 min prior to each time point during the Core Phase indicated in Table 7-6.

Table 7-6 Local ECG collection plan

Cycle	Patients	Day	Time	ECG Type
Screening	All	Day -21 to -1	Anytime	12 Lead
Cycle 1	All	Day 1	Pre-dose	12 Lead
EOT (Core Phase)	All	N/A	Anytime	12 Lead
Unscheduled san	nple as clinical	ly indicated	Anytime	12 Lead

[figure not shown]
Interpretation of the tracing must be made by a qualified physician and documented on the ECG eCRF page. Each ECG tracing should be labeled with the study number, patient initials (where regulations permit), patient number, date, and kept in the source documents at the study site. Clinically significant abnormalities present at screening should be reported on the Medical History eCRF page. Clinically significant findings must be discussed with Novartis prior to enrolling the patient in the study. New or worsened clinically significant findings occurring after informed consent must be recorded on the Adverse Events eCRF page.

Additional, unscheduled, safety ECGs may be repeated at the discretion of the investigator at any time during the study as clinically indicated. Unscheduled ECGs with clinically significant findings should be collected. Local cardiologist ECG assessment may also be performed at any time during the study at the discretion of the investigator.

7.2.2.7.2 Cardiac imaging - MUGA (multiple gated acquisition) scan or echocardiogram

The left ventricular heart function will be evaluated by ECHO or MUGA at Screening and according to the Visit Evaluation Schedule for the Core Phase as outlined respectively in Table 7-1. Additional cardiac imaging during treatment is to be performed if indicated by clinical signs or symptoms. The same imaging modality should be used.

Other assessments

No additional tests will be performed on patients entered into this study.

8 Safety monitoring and reporting

8.1 Adverse events

8.1.1 Definitions and reporting

An adverse event is defined as the appearance of (or worsening of any pre-existing) undesirable sign(s), symptom(s), or medical condition(s) that occur after patient's signed informed consent has been obtained.

Abnormal laboratory values or test results occurring after informed consent constitute adverse events only if they induce clinical signs or symptoms, are considered clinically significant, require therapy (e.g., hematologic abnormality that requires transfusion or hematological stem cell support), or require changes in study medication(s).

Adverse events that begin or worsen after informed consent should be recorded in the Adverse Events eCRF. Conditions that were already present at the time of informed consent should be recorded in the Medical History page of the patient's eCRF. Adverse event monitoring should be continued for at least 30 days following the last dose of study treatment. Adverse events (including lab abnormalities that constitute AEs) should be described using a diagnosis whenever possible, rather than individual underlying signs and symptoms. When a clear

diagnosis cannot be identified, each sign or symptom should be reported as a separate Adverse Event.

Adverse events will be assessed and graded according to the Common Terminology Criteria for Adverse Events (CTCAE) version 4.03.

If CTCAE grading does not exist for an adverse event, the severity of mild, moderate, severe, and life-threatening, death related to the AE corresponding respectively to Grades 1 - 5, will be used. Information about any deaths (related to an Adverse Event or not) will also be collected through a Death form.

The occurrence of adverse events should be sought by non-directive questioning of the patient (subject) during the screening process after signing informed consent and at each visit during the study. Adverse events also may be detected when they are volunteered by the patient (subject) during the screening process or between visits, or through physical examination, laboratory test, or other assessments. As far as possible, each adverse event should be evaluated to determine:

- 1. The severity grade (CTCAE Grade 1-5)
- 2. Its duration (Start and end dates)
- 3. Its relationship to the study treatment (Reasonable possibility that adverse event is related: No, Yes)
- 4. Action taken with respect to study or investigational treatment (none, dose adjusted, temporarily interrupted, permanently discontinued, unknown, not applicable)
- 5. Whether medication or therapy was given (no concomitant medication/non-drug therapy, concomitant medication/non-drug therapy)
- 6. Whether it is serious, where a serious adverse event (SAE) is defined as in Section 8.2.1 and which seriousness criteria have been met (include for NCDS trials)
- 7. Outcome (not recovered/not resolved, recovered/resolved, recovering/resolving, recovered/resolved with sequelae, fatal, unknown)

If the event worsens the event should be reported a second time in the eCRF noting the start date when the event worsens in toxicity. For grade 3 and 4 adverse events only, if improvement to a lower grade is determined a new entry for this event should be reported in the eCRF noting the start date when the event improved from having been Grade 3 or Grade 4.

All adverse events should be treated appropriately. If a concomitant medication or non-drug therapy is given, this action should be recorded on the Adverse Event eCRF.

Once an adverse event is detected, it should be followed until its resolution or until it is judged to be permanent, and assessment should be made at each visit (or more frequently, if necessary) of any changes in severity, the suspected relationship to the study treatment, the interventions required to treat it, and the outcome.

Progression of malignancy (including fatal outcomes), if documented by use of appropriate method (for example, as per RECIST criteria for solid tumors or as per Cheson's guidelines for hematological malignancies), should not be reported as a serious adverse event.

Adverse events separate from the progression of malignancy (example, deep vein thrombosis at the time of progression or hemoptysis concurrent with finding of disease progression) will

be reported as per usual guidelines used for such events with proper attribution regarding relatedness to the drug.

8.1.2 Laboratory test abnormalities

8.1.2.1 Definitions and reporting

Laboratory abnormalities that constitute an adverse event in their own right (are considered clinically significant, induce clinical signs or symptoms, require concomitant therapy or require changes in study treatment), should be recorded on the Adverse Events eCRF. Whenever possible, a diagnosis, rather than a symptom should be provided (e.g. anemia instead of low hemoglobin). Laboratory abnormalities that meet the criteria for Adverse Events should be followed until they have returned to normal or an adequate explanation of the abnormality is found. When an abnormal laboratory or test result corresponds to a sign/symptom of an already reported adverse event, it is not necessary to separately record the lab/test result as an additional event.

Laboratory abnormalities, that do not meet the definition of an adverse event, should not be reported as adverse events. A Grade 3 or 4 event (severe) as per CTCAE does not automatically indicate a SAE unless it meets the definition of serious as defined below and/or as per investigator's discretion. A dose hold or medication for the lab abnormality may be required by the protocol in which case the lab abnormality would still, by definition, be an adverse event and must be reported as such.

8.1.3 Adverse events of special interest

Adverse events of special interest (AESI) are defined as events (serious or non-serious) which are ones of scientific and medical concern specific to the sponsor's product or program, for which ongoing monitoring and rapid communication by the investigator to the sponsor may be appropriate. Such events may require further investigation in order to characterize and understand them.

Adverse events of special interest are defined on the basis of an ongoing review of the safety data. AESIs are discussed in detail in the Investigator Brochure.

8.2 Serious adverse events

8.2.1 Definitions

Serious adverse event (SAE) is defined as one of the following:

- Is fatal or life-threatening
- Results in persistent or significant disability/incapacity
- Constitutes a congenital anomaly/birth defect
- Is medically significant, i.e., defined as an event that jeopardizes the patient or may require medical or surgical intervention to prevent one of the outcomes listed above
- Requires inpatient hospitalization or prolongation of existing hospitalization

- Note that hospitalizations for the following reasons should not be reported as serious adverse events:
 - Routine treatment or monitoring of the studied indication, not associated with any deterioration in condition
 - Elective or pre-planned treatment for a pre-existing condition that is unrelated to the indication under study and has not worsened since signing the informed consent
 - Social reasons and respite care in the absence of any deterioration in the patient's general condition
- Note that treatment on an emergency outpatient basis that does not result in hospital admission and involves an event not fulfilling any of the definitions of a SAE given above is not a serious adverse event

8.2.2 Reporting

For patients with unknown PIK3CA status and who sign the molecular pre-screening ICF, SAE collection will start upon signing the molecular pre-screening ICF. SAEs will only be reported if the event is suspected to be causally related to a study procedure as assessed by the investigator (e.g. an invasive procedure such as biopsy). SAEs will be followed until resolution or until clinically relevant improvement or stabilization. If the main ICF is not signed (molecular screen failure), SAE collection ends 30 days after the last study related procedure.

For patients with known PIK3CA status who sign the main study ICF, SAE collection starts at time of main study informed consent whether the patient is a screen failure or not.

To ensure patient safety, every SAE, regardless of suspected causality, occurring after the patient has provided informed consent and until at least 30 days after the patient has stopped study treatment must be reported to Novartis safety immediately without undue delay, but under no circumstances later than within 24 hours of obtaining knowledge of the events (Note: If more stringent, local regulations regarding reporting timelines prevail).

Any additional information for the SAE including complications, progression of the initial SAE, and recurrent episodes must be reported as follow-up to the original episode immediately, without undue delay, but under no circumstances later than within 24 hours of the investigator receiving the follow-up information (Note: if more stringent, local regulations regarding reporting timelines prevail) An SAE occurring at a different time interval or otherwise considered completely unrelated to a previously reported one should be reported separately as a new event.

Any SAEs experienced after the 30 day safety evaluation follow-up period should only be reported to Novartis if the investigator suspects a causal relationship to the study treatment.

Information about all SAEs is collected and recorded on the Serious Adverse Event Report Form; all applicable sections of the form must be completed in order to provide a clinically thorough report. The investigator must assess and record the relationship of each SAE to each specific study treatment (if there is more than one study treatment), complete the SAE Report Form in English, and submit the completed form within 24 hours to Novartis. Detailed instructions regarding the SAE submission process and requirements for signatures are to be found in the investigator folder provided to each site.

Follow-up information is submitted in the same way as the original SAE Report. Each reoccurrence, complication, or progression of the original event should be reported as a followup to that event regardless of when it occurs. The follow-up information should describe whether the event has resolved or continues, if and how it was treated, whether the blind was broken or not, and whether the patient continued or withdrew from study participation.

If the SAE is not previously documented in the Investigator's Brochure or Package Insert (new occurrence) and is thought to be related to the Novartis study treatment, an oncology Novartis Chief Medical Office and Patient Safety (CMO&PS) department associate may urgently require further information from the investigator for Health Authority reporting. Novartis may need to issue an Investigator Notification (IN), to inform all investigators involved in any study with the same drug that this SAE has been reported. Suspected Unexpected Serious Adverse Reactions (SUSARs) will be collected and reported to the competent authorities and relevant ethics committees in accordance with Directive 2001/20/EC or as per national regulatory requirements in participating countries.

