4.1 Description of study design

This is a phase II, multicenter, open-label, three-cohort, non-comparative study of alpelisib plus endocrine therapy (either fulvestrant or letrozole) in patients (pre and post-menopausal women and men) with HR+, HER2-negative aBC harboring PIK3CA mutation(s) in the tumor, whose disease has progressed on or after prior treatments. Gonadal suppression must be achieved with either goserelin or leuprolide in men and premenopausal women patients.

Patients must have the PIK3CA mutation to be eligible for the trial as detailed in inclusion criteria. Patients will be required to sign a molecular pre-screening consent to have their mutational status either analyzed by providing adequate tumor tissue or if PIK3CA status is known, providing tumor tissue to confirm PIK3CA mutational status using a Novartis designated central laboratory. This will be conducted during a pre-screening phase prior to enrolling into the trial by Day -21. Approximately 1300 patients are expected to be pre-screened to identify PIK3CA mutational status. Those patients that harbor the PIK3CA mutation are eligible for the study and will then have the opportunity to sign the main ICF to begin screening procedures to determine eligibility.

Sign molecular pre-screening ICF
(no later than day -21)

Register in IRT

PIK3CA mutation status
for study eligibility

Yes

Local pathology report confirming status and tumor sample (archival or newly obtained)

OR

Archival or Newly obtained tumor biopsy

sample

Eligibility checklist in IRT

Figure 4-1 Pre-Screening to Screening

Pre-

Screen

Failure

Patient cohort assignment in IRT based on prior treatment with AI or fulvestrant to either:

(alpelisib + (A and C) fulvestrant or B) letrozole

Approximately 340 patients (approximately 112 in each cohort), with HR+, HER2-negative

aBC harboring a PIK3CA mutation in tumor tissue, that have progressed on or after prior treatments are expected to be enrolled. Patients will be assigned to Cohort A, B or C based on the most recent prior therapy; patients whose prior treatment is CDK 4/6 inhibitor plus fulvestrant will be enrolled in Cohort B until Cohort B enrollment is closed and then in Cohort C until it is closed for enrollment.

At the start of the Core Phase, patients will be assigned to a cohort based on previous therapy (AI or fulvestrant) as indicated below:

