7.1.1 Molecular pre-screening

After signing the molecular pre-screening consent, tumor tissue (archival or newly obtained) will be sent to a Novartis-designated central laboratory to either analyze or confirm PIK3CA mutational status. This will be conducted during a pre-screening phase prior to study screening and enrolling into the trial (all pre-screening activities must be completed by Day -21).

Patients with a pathology report indicating PIK3CA mutant status, by a certified laboratory using a validated PIK3CA mutation assay (either from tissue or blood); must still provide a tumor sample (either archival or newly obtained) to confirm PIK3CA status by a Novartis designated central laboratory.

It is recommended to provide a tumor sample collected after the most recent progression or recurrence. Tumor tissue requirements, along with shipping requirements, will be detailed in the laboratory manual provided by the central laboratory.

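### SAE collection starts at the main consent for patients with known PIK3CA status, so procedure-related SAEs between the pre-screening and main consents may go unreported in those who enter the study

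*Protocol*

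**What the plan says.** Section 8.2.2 of the protocol opens with three statements about when SAE collection begins.

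- **Unknown PIK3CA status:** "SAE collection will start upon signing the molecular pre-screening ICF". In this period the scope is restricted: "SAEs will only be reported if the event is suspected to be causally related to a study procedure as assessed by the investigator". Biopsy is the example given.
- **Known PIK3CA status:** "For patients with known PIK3CA status who sign the main study ICF, SAE collection starts at time of main study informed consent".
- **All patients:** the third paragraph requires prompt reporting of "every SAE, regardless of suspected causality, occurring after the patient has provided informed consent", up to at least 30 days after study treatment stops. It does not say which consent is meant.

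Known-status patients are not exempt from pre-screening. Section 4.1 says "Patients will be required to sign a molecular pre-screening consent" and extends this to the case where, "if PIK3CA status is known, providing tumor tissue to confirm PIK3CA mutational status using a Novartis designated central laboratory", the consent serves central confirmation. Section 7.1.1 adds that patients with a local mutation report "must still provide a tumor sample (either archival or newly obtained) to confirm PIK3CA status by a Novartis designated central laboratory", and places this before screening, to be finished by Day -21.

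**The concern.** Both groups sign the same pre-screening consent and may have the same invasive sampling under it. Section 2.6.3 lists fresh tumor sampling among the study-related risks. Section 8.2.2 covers the resulting serious complications for one group from the pre-screening consent and for the other only from the main consent, and gives no reason for the difference.

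At stake is completeness of safety reporting for a procedure the study itself may prompt. A site that follows the status-specific sentence would not report a serious biopsy complication in a known-status patient before the main consent. A site that follows Table 7-1 might record it. If no pre-screening SAEs appear for known-status patients, a reader could not tell whether none occurred or none were collected.

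**Working it through.** No arithmetic applies. The check sets the relevant statements side by side and then follows each type of patient through them.

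| Place in protocol | Who | Start | Scope |
|---|---|---|---|
| 8.2.2, paragraph 1 | Unknown status | Pre-screening consent | Procedure-related SAEs |
| 8.2.2, paragraph 2 | Known status, main consent signed | Main consent | SAEs |
| 8.2.2, paragraph 3 | All | Informed consent, not specified | All SAEs, any cause |
| 7.1.2.2 | Molecular pre-screening failures, no split by status | Pre-screening | Procedure-related SAEs |
| Table 7-1, adverse events row | All | Marked at pre-screening and screening, for the database | Adverse events, with reference to 8.1 |
| 8.1.1 | All | Informed consent, not specified | Adverse events |

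Section 11.3 lists the pre-screening consent and the main consent as separate informed consents, so the unspecified term in 8.1.1 and 8.2.2 could mean either.

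**By type of patient**

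1. Unknown status: covered from the pre-screening consent for procedure-related SAEs.
2. Known status, archival tissue: no new sampling, so no biopsy complication to miss.
3. Known status, new sample, main consent never signed: 8.2.2 equates this with a molecular screen failure, and 7.1.2.2 covers such failures whatever their status.
4. Known status, new sample taken only after the main consent: covered from that consent.
5. Known status, new sample between the two consents, main consent signed later: paragraph 2 starts too late, paragraph 1 is limited to unknown status, and 7.1.2.2 does not apply because the patient is not a failure.

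Only type 5 is exposed.

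**Does another provision close the gap for type 5?**

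- *Paragraph 3 of 8.2.2.* If it means the main consent, the gap remains. If it means the pre-screening consent, the gap closes, but all SAEs of any cause would then be reportable in pre-screening. That contradicts the procedure-related limit in paragraph 1 and in 7.1.2.2, and the later start in paragraph 2.
- *Table 7-1.* It shows an intention to collect adverse events at pre-screening without regard to status. It refers to 8.1, not to the SAE rule in 8.2.2, so it conflicts with paragraph 2 without overriding it.
- *A different meaning of known status.* If it means known by the time of the main consent, a patient who arrives with a local report is still not of unknown status at pre-screening, so paragraph 1 still does not apply.

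**The case against.** The strongest reply is that the protocol does provide for pre-screening events. Table 7-1 marks them for the database, 7.1.2.2 reports procedure-related SAEs in pre-screening failures, and the general sentence in 8.2.2 can be read to include the pre-screening consent. A reader might infer from the status-specific sentence that biopsy-related SAEs in known-status patients are simply missed. The documents do not support that, because these provisions point the other way. They also do not settle the matter, for the reasons given in the check. What stands is that reporting in this interval is uncertain and may differ between sites.

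The sequence is also not fixed. Section 7.1.2 lets screening proceed on a certified laboratory's report, and 7.1.5.1 provides for replacing patients who enter on a local report without central confirmation. A sample need not always precede the main consent. Nor is a newly obtained sample necessarily a biopsy done for the study; a sample from after the latest progression is recommended, not required. This narrows the group but does not empty it, since 4.1 and 7.1.1 place tissue submission in pre-screening.

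Finally, enrollment was complete as of 14-Dec-2020 with 380 patients, and Amendment 6 is dated 28-Mar-2023. An edit now protects no further patient at pre-screening. That is correct and limits the value of the change to a consistent rule and a correct reading of the data.

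**Conclusion.** The concern holds in limited form. The status-specific rule in 8.2.2 leaves the interval between the two consents uncovered for known-status patients who give a new sample in that interval and later sign the main consent. Procedure-related SAEs there may go unreported. The rule is at odds with Table 7-1, and the general sentence in 8.2.2 cannot resolve this while its consent is undefined.

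The size cannot be stated. The protocol expects about 1300 patients to be pre-screened but does not say how many would arrive with a local report or how many of those would give new tissue. Serious complications within that subset would be a smaller number again. The primary endpoint, sample size and error rate are unaffected, as are the on-treatment safety summaries, which begin at first dose. This is a minor point of safety reporting.

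The conclusion assumes that at least some known-status patients had tissue newly taken after the pre-screening consent and before the main consent. The documents allow this but do not show how often it happened.

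**What to change.** Reconcile 8.2.2, 7.1.2.2 and Table 7-1 with one rule for everyone who signs the pre-screening consent, whatever their PIK3CA status: SAEs suspected to be related to a study procedure are collected from that consent, and all SAEs from the main consent. In the third paragraph of 8.2.2, state which consent is meant. This extends the sponsor's own rule for unknown-status patients to the same procedure in the others, and costs about two sentences.

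Because enrollment is complete, also state in the CSR which start rule sites applied to known-status patients. The absence of pre-screening SAEs in that group should not be read as an absence of events unless collection was in force. This adds a short statement to the CSR and no new analysis.
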